### **6.6.8. ECOG performance status**

The ECOG shift from baseline to highest score during the on-treatment period will be summarized by treatment arm. ECOG performance status with shift from ECOG=0 or 1 to ECOG 2 or higher will also be presented in a data listing.

## **7. INTERIM ANALYSES**

### **7.1. Introduction**

The goals of the interim analyses are to allow early stopping of the study for futility or to do an early determination of superiority of Arm A compared to Arm B based on PFS. The interim analysis of PFS and OS will be performed as described in Sections 5.1.1 and 5.1.2 using the methodology described in Section 6.1.1 for PFS and Section 6.2.2.1 for OS.

At the time of the interim analysis for PFS, the interim analysis for OS will be performed by an independent statistician. Unblinded results from the interim analysis for PFS and first interim analysis for OS will not be communicated to the Sponsor's clinical team or to any party involved in the study conduct (apart from the independent statistician and E-DMC members) until the E-DMC has determined that either (i) PFS analysis has crossed the pre-specified boundary for efficacy or (ii) the study needs to be terminated due to any cause, including futility or safety reasons. Further details will be described in the E-DMC charter.

At the time of final PFS analyses, both PFS and interim OS analysis will be performed by the Sponsor's clinical team. All patients will continue to be followed for OS until the final OS analysis (or earlier if OS reaches statistical significance at an interim analysis).

### **7.2. Interim Analyses and Summaries**

At each analysis time point, the critical boundaries for the group sequential test will be derived from the predefined spending function(s) as described in Section 5.1. The calculations of boundaries will be performed using EAST.

#### **7.2.1. Interim analysis for PFS**

Let  $u(t_1)$  and  $u(t_F)$  denote the upper critical boundaries based on the test statistics  $Z_1$  and  $Z_F$  for efficacy at the interim and the final analysis, respectively, and let  $l(t_1)$  and  $l(t_F)$  denote the lower critical boundary for futility at the interim and final analysis, respectively. For the final analysis,  $l(t_F)=u(t_F)$ .

The critical values  $u(t_1)$  and  $l(t_1)$  for the interim analysis of PFS are determined such as

$$P_0(Z_1 \geq u(t_1)) = \alpha(t_1) \quad \text{and} \quad P_a(Z_1 \leq l(t_1)) = \beta(t_1),$$

where  $P_0$  and  $P_a$  denote the probabilities under the null hypothesis and the alternative hypothesis, respectively, and  $\alpha(t_1)$  and  $\beta(t_1)$  denote the  $\alpha$  and  $\beta$  spent, respectively, based on

the predefined spending functions at information fraction  $t_1$  ( $t_1$  is calculated as the ratio of the number of PFS events observed at the time of the cut-off for the interim analysis and the total number of PFS events targeted for the final analysis).

The boundary for the final efficacy analysis will be calculated such that

$$\alpha(t_1) + P_0(Z_1 < u(t_1), Z_F \geq u_F) = 0.025$$

As described in Section 5.1.2, if the number of PFS events in the final analysis deviates from the target number of PFS events, the final analysis criteria will be determined as above taking into account the actual alpha spent at the interim analysis and the actual correlation between the two test statistics  $Z_1$  and  $Z_F$ , so that the overall 1-sided significance level across all analyses and comparisons is preserved at 0.025.

### 7.2.2. Interim analysis for OS

No futility analysis will be performed for OS. Let  $u(t_i)$  and  $u(t_F)$  denote the upper critical boundaries based on the test statistics  $Z_i$  and  $Z_F$  for efficacy at the  $i^{\text{th}}$  interim and the final analysis, respectively, where  $i=1, 2, 3, 4$ .

In what follows  $P_0$  denotes the probability under the null hypothesis, and  $\alpha(t_i)$  denotes the  $\alpha$  spent based on the predefined  $\alpha$ -spending function at information fraction  $t_i$  ( $t_i$  is calculated as the ratio of the number of OS events observed at the time of the cut-off for the  $i^{\text{th}}$  interim analysis and the total number of OS events targeted for the final analysis).

For each comparison, the critical value  $u(t_1)$  for the 1st interim analysis of OS is determined such as

$$P_0(Z_1 \geq u(t_1)) = \alpha(t_1).$$

Critical boundaries for the additional interim analyses and the final analysis of OS are calculated recursively as follows for each comparison

$$u(t_2) \text{ is derived such that } \alpha(t_1) + P_0(Z_1 < u(t_1), Z_2 \geq u(t_2)) = \alpha(t_2),$$

$$u(t_3) \text{ is derived such that } \alpha(t_2) + P_0(Z_1 < u(t_1), Z_2 < u(t_2), Z_3 \geq u(t_3)) = \alpha(t_3),$$

$$u(t_4) \text{ is derived such that } \alpha(t_3) + P_0(Z_1 < u(t_1), Z_2 < u(t_2), Z_3 < u(t_3), Z_4 \geq u(t_4)) = \alpha(t_4).$$

The boundary for the final efficacy analysis is derived such that

$$\alpha(t_4) + P_0(Z_1 < u(t_1), Z_2 < u(t_2), Z_3 < u(t_3), Z_4 < u(t_4), Z_F \geq u_F) = 0.025.$$

As described in Section 5.1.2, if the number of OS events in the final analysis deviates from the target number of OS events, the final analysis criteria will be determined as above taking into account the actual alpha spent at the interim analyses and the actual correlation between the four test statistics  $Z_i$  ( $i=1, 2, 3, 4$ ) and  $Z_F$ , so that the overall 1-sided significance level across all analyses and comparisons is preserved at 0.025.

## 9. APPENDICES

### Appendix 1. Immune-Related Adverse Events

The MedDRA PTs and clusters for irAEs are defined in the SRP for avelumab.

Immune-related AEs (irAEs) will be programmatically identified as outlined in Table 24. This case definition is hierarchical, ie, each step is only checked for patients and events that have already met the prior step.

**Table 24. Case Definition for irAEs**

Step	Selection Criteria	Additional Notes
1	Event selected based on a list of pre-specified MedDRA PTs within clusters. These are included in the SRP as Tier1 events (Immune-mediated xxxx). If AE matches the list, then it is in for the next step.	
2	AE onset during 1 st study drug administration or anytime thereafter through 90 days after last dose of study treatment.	This is regardless of start of new anti-cancer drug therapy and regardless of TEAE classifications
3	Answer in the AE eCRF page to ‘Was another treatment given because of the occurrence of the event’ is ‘YES’	
4	AE treated with corticosteroids or other immunosuppressant therapy. For endocrinopathies only: AE required hormone replacement	Look in the conmed pages for AE identifiers that match the AEs from Step 3. For each of such AEs if A) OR B) OR C) below are met then the AE is in for the next step A) conmed ATC code is in (H02A, H02B, D07, A01AC, S01BA, S01BB, L04AA, L04AB, L04AC, L04AD, L04AX, A07EA) and AE PT is in any of the irAE clusters. B) conmed ATC code is in (H03A, H03B) and AE PT is in one of the irAE clusters associated with “Immune-mediated endocrinopathies” C) conmed ATC code is A10A and AE PT is in the irAE cluster associated with “Immune-mediated endocrinopathies: Type I Diabetes Mellitus”

5	
A) No clear etiology (other than immune mediated etiology)
 
B) Histopathology / biopsy consistent with immune-mediated event
 
Event is in if          [Answer to 5B1 and 5B2 is YES (regardless of answer to 5A)]          OR          [Answer to 5B1 is YES AND answer to 5B2 is NO AND answer to 5A is NO]          OR          [Answer to 5B1 is NO AND answer to 5A is NO]
	
A) From the AE eCRF page.          Is the AE clearly related to an etiology other than immune-mediated etiology? Yes / No          If answer is Yes, check all that apply:
 
 
• Underlying malignancy / progressive disease.
 
• Other medical conditions.
 
• Prior or concomitant medications / procedures.
 
• Other. Specify.
 
 
B) From the AE eCRF page.          B1) Was there a pathology /histology evaluation performed to investigate the AE? Y/N          B2) If answer to the above is Yes, does the pathology/histology evaluation confirms an immune mediated mechanism for the AE? Y/N          B3) If pathology / histology evaluation performed to investigate the AE, provide summary of relevant findings of the pathology /histology report. (Free Text)

---	---	--

The data set associated with irAEs may be refined based on medical review. The final data set including any changes based on medical review (eg, addition of cases that are not selected by the programmatic algorithm) will be the basis of the irAE analyses.

## Appendix 2. Infusion Related Reactions

For defining an AE as IRR the onset of the event in relation to the infusion of study drug and time to resolution of the event will be considered.

- All AEs identified by the MedDRA PT query describing signs and symptoms will be considered potential IRRs when onset is on the day of study drug infusion (during or after infusion) and the event resolved with end date within 2 days after onset.
- All AEs identified by the MedDRA PTs of Infusion related reaction, Drug hypersensitivity, Anaphylactic reaction, Hypersensitivity, Type 1 hypersensitivity, will be considered potential IRRs when onset is on the day of study drug infusion (during or after the infusion) or the day after the study drug infusion (irrespective of resolution date).

The list of MedDRA PTs for ‘IRRs SIGNS and SYMPTOMS’ and PTs ‘IRRs CORE’ are defined in the SRP for avelumab.

Infusion-related reactions (IRRs) will be programmatically identified as outlined in Table 25 or Table 26 and will be identified for IV drugs only.

**Table 25. Case Definition for IRRs – IV Study Drugs Administered Alone Or In Combination With Non-IV Study Drugs**

Condition	Selection criterion
If AE meets [1 AND 2] OR [3 AND (4A OR 4B)] then AE is classified as an IRR	
1	PT is included in the ‘IRRs SIGNS and SYMPTOMS’ list
2	
 
• AE onset date = date of infusion of study drug AND
 
• AE timing related to study drug (‘DURING’, ‘AFTER’) AND
 
• AE outcome in (‘RECOVERED/RESOLVED’, ‘RECOVERED/RESOLVED WITH SEQUELAE’, ‘RECOVERING/RESOLVING’) AND
 
• AE end date – AE onset date <=2
 

3	PT is included in the ‘IRRs CORE’ list
4A	
 
• AE onset date = date of infusion of study drug AND
 
• AE timing related to study drug in (‘DURING’, ‘AFTER’)
 

4B	AE onset on the day after infusion

**Table 26. Case Definition for IRRs – IV Study Drugs Administered in Combination (eg, Doublets or Triplets)**

Condition	Selection criterion
	
IRR can be associated with the first IV drug and/or subsequent IV drugs that are administered in combination. Without loss of generality assume triplet IV with D1 administered first then D2 then D3. The IV study drug or drugs associated with the IRR need to be identified in the analysis data set to enable subsequent analysis.
 
The following are not sequential and an AE can be classified as an IRR associated with multiple DJ from one or more of I, II, III, IV, V below:
 
I - If the AE meets [1 AND 2A1] for a DJ then the AE is classified as an IRR associated with the DJ that meets the 2A1 criterion
 
II - If the AE meets [1 AND 2A2] for a DJ then the AE is classified as an IRR associated with the DJ and associated with DJ+1 that meets the 2A2 criterion
 
III - If the AE meets [3 AND 4B] for any DJ then the AE is classified as an IRR associated with all DJ that meet the 4B criterion.
 
IV- If the AE meets [3 AND 4A1] for a DJ then the AE is classified as an IRR associated with the DJ that meets the 4A1 criterion
 
V- If the AE meets [3 AND 4A2] for a DJ then the AE is classified as an IRR associated with the DJ and associated with DJ+1 that meets the 4A2 criterion

1	PT is included in the ‘IRRs SIGNS and SYMPTOMS’ list
2A1	
 
• AE onset date = date of infusion of study drug DJ AND
 
• AE timing related to study drug DJ (‘DURING’, ‘AFTER’) AND
 
• [AE timing related to study drug DJ+1 (‘BEFORE’) OR AE onset date < date of infusion of study drug DJ+1] AND
 
• AE outcome in (‘RECOVERED/RESOLVED’, ‘RECOVERED/RESOLVED WITH SEQUELAE’, ‘RECOVERING/RESOLVING’) AND
 
• AE end date – AE onset date <=2
 

2A2	
 
• AE onset date = date of infusion of study drug DJ AND
 
• AE timing related to study drug DJ (‘DURING’, ‘AFTER’) AND
 
• AE timing related to study drug DJ+1 (‘DURING’, ‘AFTER’) AND
 
• AE outcome in (‘RECOVERED/RESOLVED’, ‘RECOVERED/RESOLVED WITH SEQUELAE’, ‘RECOVERING/RESOLVING’) AND
 
• AE end date – AE onset date <=2
 

3	PT is included in the ‘IRRs CORE’ list
4A1	
 
• AE onset date = date of infusion of study drug DJ AND
 
• AE timing related to study drug DJ (‘DURING’, ‘AFTER’) AND
 
• [AE timing related to study drug DJ+1 (‘BEFORE’) OR AE onset date < date of infusion of study drug DJ+1]
 

4A2	
 
• AE onset date = date of infusion of study drug DJ AND
 
• AE timing related to study drug DJ (‘DURING’, ‘AFTER’) AND
 
• AE timing related to study drug DJ+1 (‘DURING’, ‘AFTER’)
 

4B	AE onset on the day after infusion of study drug D J

### **Appendix 3. Programmatic Derivation of Tumor Response Using RECIST v1.1**

#### Methods of Tumor Assessment

The following are considered “interchangeable” methods: Conventional CT, Spiral CT, Enhanced CT, MRI and Enhanced MRI.

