11. **Tumor Assessments:** Tumor assessments will include all known or suspected disease sites. The CT and MRI scans should be performed with contrast agents unless contraindicated for medical reasons. The same imaging technique(s) used to characterize each identified and reported lesion at baseline will be employed in the following tumor assessments. At minimum, the CT modality used at baseline will be the expected imaging technique for follow-up. Additional imaging modalities may also be employed if clinically required. Radiographic and clinical evaluations will be conducted with the same schedule in both treatment arms of the study. The investigator will assess antitumor activity based on radiological assessments and clinical evaluation of patients using modified RECIST v1.1 12 weeks after the completion of CRT, every 16 weeks thereafter for 48 months (208 weeks), and every 24 weeks thereafter until confirmed disease progression per modified RECIST v1.1 and regardless of discontinuation of study treatment or initiation of subsequent anti-cancer therapy. Radiological tumor assessments will also be conducted whenever disease progression is suspected (eg, symptomatic deterioration or physical exam findings suggestive of mucosal recurrence). The assessment performed 12 weeks after completion of the CRT is to include CT and PET for all patients and MRI also if clinically appropriate to delineate the extent of the local tumor. Subsequent scans are to include CT of the head and neck and thorax. In the case of negative PET in patients who did not achieve clinical or CT/MRI-based radiological nodal CR at the tumor assessment performed 12 weeks following completion of CRT, follow-up PET scans are recommended every 4 months (16 weeks) with the CT imaging for 24 months (104 weeks), then every 6 months (24 weeks) in Years 3-5. CT imaging should be obtained as described herein beyond Year 5. The time window for tumor assessments is  $\pm 1$  week except for the assessment at week 12 which cannot be done earlier but up to one week later.

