### 7.8. Tumor Response Assessment

Tumor assessments will include all known or suspected disease sites. Imaging at screening (baseline) and at 12 weeks after completion of CRT must include a head and neck CT or MRI, chest CT, and PET scan. High resolution PET/CT does not require additional CT thorax/neck/brain. MRI brain may be performed if clinically indicated. Other areas may be scanned as clinically indicated. The CT and MRI scans should be performed with contrast agents unless contraindicated for medical reasons. The same imaging technique used to characterize each identified and reported lesion at baseline will be employed in the following tumor assessments. At a minimum, the CT modality used at baseline will be the expected imaging technique for follow-up. Any clinical progression concern warranting a biopsy must have supporting imaging (ie, CT, MRI, PET, or digital photograph) archived for documentation purposes. Additional imaging modalities may also be employed if clinically required. Baseline tumor assessments should be done within 28 days prior to randomization.

Radiographic and clinical evaluations will be conducted with the same schedule in both treatment arms of the study. The investigator will assess antitumor activity based on radiological assessments and clinical evaluation of patients using modified RECIST v1.1 ([Appendix 3](#)) at screening (baseline), 12 weeks after the completion of CRT, every 16 weeks thereafter for 48 months (208 weeks), and every 24 weeks (Q24W) thereafter until confirmed disease progression per modified RECIST v1.1 and regardless of discontinuation of study treatment or initiation of subsequent anti-cancer therapy.

The assessment performed 12 weeks after completion of the CRT is to include CT and PET for all patients and MRI also if clinically appropriate in patients who did not achieve clinical or CT/MRI-based radiological nodal CR at the tumor assessment performed 12 weeks following completion of CRT, and follow-up PET scans are recommend every 4 months (16 weeks) with the CT imaging for 24 months (104 weeks), then every 6 months (Q24W) in Years 3-5. CT imaging should be obtained as described in the [Schedule of Activities](#) beyond Year 5. The time window for tumor assessments is  $\pm 1$  week except for the assessment at Week 12 which cannot be done earlier but can be done up to one week later.

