#### Evaluation of Target Lesions at Each Visit

- The sum of lesion dimensions (SLD) is only considered if the methods of assessments are consistent with baseline. The “interchangeable” methods noted above are all considered consistent methods.
- In the SLD, the longest diameter will be used for non-nodal lesions and the short axis dimension will be used for each lymph node included in the sum.
- Complete Response (CR) is defined by the disappearance of all non-lymph node target lesions (where all target lesions are recorded with a length of 0 mm on the “Target Lesions” eCRF). Any pathological lymph nodes (recorded as target lesion) must have reduction in short axis to <10 mm. Note: the SLD may not be zero if lymph nodes are included as target lesions.
- Partial Response (PR) is defined by a 30% or more decrease in SLD of target lesions, taking as reference the baseline SLD.
- Progressive Disease (PD) is defined by a 20% or more increase in the SLD of target lesions relative to nadir (smallest SLD considering baseline and all assessments prior to the timepoint under evaluation), with a minimum absolute increase of 5 mm relative to nadir.
  - If only a subset of target lesions are assessed and the sum of the non-missing lesion diameters results in an increase above of at least 5 mm and at least 20% above the nadir, then the progression criteria will have been met.
- Stable Disease (SD) is assigned when neither sufficient shrinkage to qualify for CR or PR, nor sufficient increase to qualify for PD is observed, taking as reference the nadir.
- No Target Lesion at Baseline (NB) is assigned if “No Target Lesion” is checked, on the “Target Lesions” eCRF.
- Not All Evaluated (NAE) is assigned if:
  - Any individual target lesion is evaluated as “Indeterminate” on the “Target Lesions” eCRF
  - Inconsistent methods are used for any target lesions after randomization
  - One or more target lesions are not assessed

- One or more target lesions were excised or irradiated and have not reappeared or increased.

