#### Objective Response Status At Each Assessment

- Overall response is determined from the derived target and non-target lesion data using conventions in Table 27 under the assumption that there are no new lesions identified at the visit. **If there are any new lesions at a time point, then the response is PD at that time point regardless of target or non-target lesion response.**
- Objective status after a change in modality that is not considered interchangeable is classified as NE.

- To group target and non-target lesion measurements to the corresponding actual post-baseline tumor assessment visit, a clustering algorithm is applied. Each cluster represents an actual visit. For each patient, the number of clusters is equal to the maximum number of assessments available among all target and non-target lesions. The SAS procedure, Proc Fastclus, is applied to a variable that represents the days from randomization to the date of the scan for lesion (date of scan – randomization +1). Then the assessments of lesions (target, non-target, new) that occurred close to each other in time will be assigned to the same cluster.

The rules for derived objective status for each visit are presented in Table 27.

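### SAP Appendix 3 does not list PET/CT as interchangeable with CT, so a protocol-compliant PET/CT baseline could make later CT visits not evaluable in the derived standard-RECIST analyses

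*SAP*

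**What the plan says.** **Protocol.** Section 7.8 sets the imaging for the two key visits: "Imaging at screening (baseline) and at 12 weeks after completion of CRT must include a head and neck CT or MRI, chest CT, and PET". It then adds: "High resolution PET/CT does not require additional CT thorax/neck/brain". The same permission is in Section 3.2 and in the tumor-assessment footnote to Table 2. After week 12, Table 3 footnote 11 moves follow-up to CT: "Subsequent scans are to include CT of the head and neck and thorax". That footnote also asks for continuity of technique: "The same imaging technique(s) used to characterize each identified and reported lesion at baseline will be employed in the following tumor assessments", and "At minimum, the CT modality used at baseline will be the expected imaging technique for follow-up".

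**SAP Appendix 3** derives standard RECIST v1.1 status by program. Its interchangeable methods are "Conventional CT, Spiral CT, Enhanced CT, MRI and Enhanced MRI". The target-lesion sum, and the non-target categories including progression, are used only when the method is consistent with baseline. Target lesions become Not All Evaluated if "Inconsistent methods are used for any target lesions after randomization", and non-target lesions have a matching rule. At visit level, "Objective status after a change in modality that is not considered interchangeable is classified as NE". A new lesion is progression whatever the method.

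**Where the derivation is used.** It feeds S0 to S4 (SAP 6.2.2.2), best overall response, objective response, duration of response and time to response per derived standard RECIST (SAP 6.2.2), and the S0-based comparison of modified with standard RECIST.

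**The concern.** Baseline PET/CT followed by CT is a route the protocol allows, not a deviation. Read literally, Appendix 3 handles it as a change of modality and discards the comparison.

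The standard-RECIST sensitivity analysis and its discordance summary are the checks that Protocol 9.3.1 names for the modified primary endpoint. If real growth is classed as not evaluable because of a method label, some patients would appear as events under modified RECIST and non-events under standard RECIST. A reader would attribute that disagreement to the modified criteria when it came from the program.

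Protocol Appendix 4 lets a radiologist decide whether a changed technique can be substituted. The SAP program has no such step.

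**Working it through.** The plan gives no figure on this point, so the check applies the written rules to each modality sequence. It assumes that PET/CT is recorded as its own method and that an unchanged method counts as consistent.

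**Step 1. Status at a single visit** (SAP Appendix 3 consistency rules, Table 27, new-lesion override):

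| Baseline → visit | Target growth | Non-target increase | Stable | New lesion |
|---|---|---|---|---|
| CT → CT or MRI | PD | PD | SD | PD |
| PET/CT → PET/CT | PD | PD | SD | PD |
| PET/CT → CT or MRI | NE | NE | NE | PD |
| CT → PET/CT | NE | NE | NE | PD |

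If the CT part is recorded as one of the listed CT types, every row behaves like the first.

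**Step 2. PET/CT-only baseline, then CT.** The first post-baseline scan falls at about week 1 + 7 + 12 = 20 and the next at about 20 + 16 = 36.
- Under SAP 5.2.11, NE visits do not set the censoring date. In S0 (Table 13), an event-free patient with only NE visits is censored at randomization. If week 12 after chemoradiotherapy was also PET/CT, that visit is evaluable and the loss starts at the next CT.
- In S1 (Table 14), progression or death after two or more indeterminate visits is censored unless it falls within 36 weeks of randomization. Here even a later new lesion or death can be lost.
- In S0 and S2 to S4, new lesions and deaths remain events. Only progression shown by growth alone is exposed.

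**Step 3. CT baseline, PET/CT at week 12, CT thereafter.** Consistency is judged against baseline, so only the week-12 visit is NE and later CT visits are evaluable. The week-12 sum is not considered, however, and so cannot serve as nadir. An illustration with sums of 50 mm (baseline), 20 mm (week 12) and 30 mm (next CT):
- Week-12 sum kept: (30 − 20)/20 = +50% and +10 mm from nadir, which is PD (thresholds 20% and 5 mm).
- Week-12 sum dropped: (30 − 50)/50 = −40% from baseline, which is PR.

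**Step 4. Possible scale.** The documents give neither the share of patients with PET/CT-only baselines nor the share of events shown by growth alone. With both assumed, and the 289 target events as a convenient base (that target is for modified RECIST), events exposed through Step 2 = 289 × PET/CT-only share × growth-only share:
- 5% and 10%: 289 × 0.05 × 0.10 = 1.4
- 20% and 25%: 289 × 0.20 × 0.25 = 14.5
- 40% and 50%: 289 × 0.40 × 0.50 = 57.8

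If the CT part is coded as CT, the figure is 0. These are illustrations, not estimates.

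**The case against.** The strongest reply is that the CT part of a PET/CT is already CT. Protocol Appendix 4 defines measurable disease by CT or MRI, chest X-ray or caliper, and does not name PET/CT, so a lesion sized on PET/CT is most naturally sized on its CT images. The protocol's waiver of additional CT treats that component as meeting the CT requirement, and "At minimum, the CT modality used at baseline will be the expected imaging technique for follow-up" can be read the same way. On this reading, PET/CT then CT is CT then CT, which Appendix 3 accepts. This is a sensible reading and may be what sites do. But neither document states it or says how the eCRF codes the method. A program acts on the recorded value.

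It is also fair that the stakes are limited. Primary PFS uses investigator progression per modified RECIST, the SAP calls these sensitivity analyses purely exploratory, and S0_B and M1_B use central review. The response endpoints are also analysed per modified RECIST. The trial is double-blind with the same imaging schedule in both arms, so no bias in favour of either arm is shown. All of this stands, and it limits the point's importance without closing the gap.

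A reader might infer that nearly all of an affected patient's event risk is lost, because the planned medians of 33 and 48.5 months put only 1 − exp(−ln 2 × 4.6/33) = 9% and 1 − exp(−ln 2 × 4.6/48.5) = 6% of PFS events before week 20 (4.6 months). The documents do not support that. The calculation counts all PFS events, including the deaths and new lesions that S0 and S2 to S4 retain.

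**Conclusion.** The gap is real but its effect is conditional. As written, Appendix 3 misclassifies a protocol-compliant imaging route if PET/CT is recorded as its own method. A PET/CT-only baseline then removes growth-based progression at later CT visits from S0 to S4 and from the derived standard-RECIST response endpoints. A week-12 PET/CT after a CT baseline costs one visit and its nadir.

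Two stronger readings should be resisted. It is not shown that later CT scans will be not evaluable, since that depends on eCRF coding absent from both documents. Nor does a week-12 PET/CT by itself spoil later CT visits.

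The size ranges from nothing upward and cannot be fixed from the documents. Primary PFS, OS, S0_B and M1_B are unaffected. The change is worth making because it protects the protocol's own check on its modified endpoint.

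**What to change.** In SAP Appendix 3, under the methods of tumor assessment, add the CT component of a high-resolution PET/CT to the interchangeable methods. State that such scans, at baseline or at week 12, are treated as CT in the method-consistency check for target and non-target lesions. Confirm which eCRF method value this corresponds to.

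The cost is one line of SAP text and one value in the program, with no new data. It should be settled before unblinding so that it cannot be seen as a post hoc choice. If sites already record the CT part as CT, no result changes.
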